8.5.6. Booster Phase Analysis

8.5.6.1. Part 1C-1 – Homologous Booster Phase

Booster Phase analysis will be performed in participants who receive a BD in Part 1C-1. Safety, immunogenicity endpoints, and incidence of COVID-19 and SARS-CoV-2 infection will be summarized descriptively, and by prebooster SARS-CoV-2 status if applicable.

In the Booster Phase safety analysis, the number and percentage of participants with unsolicited AEs, severe AEs, treatment-related AEs, SAEs, MAAEs, AESIs, and AEs leading to discontinuation from the study participation in Part 1C-1 will be summarized.

The number and percentage of participants with any solicited local AR, with any solicited systemic AR, and with any solicited AR during the 7-day follow-up period after the BD will be provided.

In the Part 1C-1 Booster Phase, for the coprimary endpoints (Ab GM value and SRR against the ancestral strain) and key secondary endpoints (Ab GM value and SRR against the circulating strain), the following analyses will be performed for the respective hypothesis testing:

- The GM titers with 95% CI will be summarized using t-distribution of the log transferred values and then back transformed to the original scale. The GMR with 95% CI to compare postbooster GM value at BD-Day 29 in adolescents in Study P203 with the primary series GM value at Day 57 (28 days after Dose 2) in young adults (18 to 25 years of age) in Study P301 will be computed based on the t-distribution of mean difference in the log transferred values and then back transformed to the original scale.
- The SRR with 95% CI (using Clopper-Pearson method) will be summarized. The SRR difference with 95% CI (using Miettinen-Nurminen score method) to compare postbooster SRR at BD-Day 29 in adolescents in Study P203 with the primary series SRR at Day 57 (28 days after Dose 2) in young adults in Study P301 will be computed. Seroresponse is defined as Ab value change from baseline (pre Dose 1) below the LLOQ to $\geq 4 \times$ LLOQ, or at least a 4-fold rise if baseline is \geq LLOQ.

In the Booster Phase immunogenicity analyses, the GM titers or levels for specific nAb and bAb, with corresponding 95% CI will be provided at BD-Day 1, BD-Day 29, BD-Day 181, and BD-Day 361 (Part 1C-1). GMFR relative to pre Dose 1, (Homologous Booster) BD-Day 1 and prior Day 57 in the phase of primary 2-dose series of mRNA-1273 will be summarized with 95% CIs at BD-Day 29, BD-Day 181, and BD-Day 361 (Part 1C-1). The 95% CIs will be calculated

based on the t-distribution of the log transformed values then back transformed to the original scale. Descriptive summary statistics including median, minimum, and maximum will also be provided. The immunogenicity descriptive summaries will be provided in the participants who have available nAb and bAb assay results for the specified timepoints.

In the Booster Phase, the incidence rate of the first occurrence of symptomatic COVID-19 starting 14 days after the BD will be summarized by prebooster SARS-CoV-2 status. The incidence rate of SARS-CoV-2 infection (symptomatic or asymptomatic infection) starting 14 days after the BD, and the incidence rate of asymptomatic SARS-CoV-2 infection starting 14 days after the BD will be summarized. The incidence rates with 95% CI will be computed adjusting for person-years starting from BD-Day 1 in Part 1C-1.

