
 • To evaluate the incidence of SARS-CoV-2 infection or COVID-19 after vaccination with mRNA-1273 	
 • The incidence of SARS-CoV-2 infection (symptomatic or asymptomatic infection) counted starting 14 days after BD of mRNA-1273 • To evaluate the incidence of asymptomatic SARS-CoV-2 infection after vaccination with mRNA-1273 measured by RT-PCR and/or bAb levels against SARS-CoV-2 nucleocapsid protein (by Roche Elecsys) counted starting 14 days after

Objectives	Endpoints
	
BD in participants with negative SARS-CoV-2 at baseline or prebooster
 
 The incidence of the first occurrence of symptomatic COVID-19 starting 14 days after BD of mRNA-1273
Objectives for Part 1C-2 – Heterologous Booster Dose	Endpoints for Part 1C-2 – Heterologous Booster Dose
Primary Objectives	Primary Endpoints

 To evaluate the safety of the 50 µg BD of mRNA-1273 in participants who received non-Moderna COVID-19 primary series vaccination 	
 Solicited local and systemic ARs through 7 days after BD Unsolicited AEs through 28 days after BD injection MAAEs through the entire study period SAEs through the entire study period AESIs through the entire study period AEs leading to discontinuation from study participation post BD through the last day of study participation

 To evaluate immune response elicited by the 50 µg booster of mRNA-1273 in participants who received non-Moderna COVID-19 primary series vaccination 	
 GM value of postbooster Ab (BD-Day 29) against ancestral strain
Key Secondary Objective	Key Secondary Endpoint

 To evaluate immune response elicited by the 50 µg prototype booster of mRNA-1273 against variant(s) of interest in participants who received non-Moderna COVID-19 primary series vaccination 	
 GM value of postbooster Ab (BD-Day 29) against circulating strain
Exploratory Objectives	Exploratory Objectives

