3.1.1.3. Part 1C-1, Homologous Booster Phase

Part 1C-1 Homologous Booster Phase is designed to offer participants in Part 1A and Part 1B, who are at least 5 months from the last dose, the option to request a BD (50 µg) of mRNA-1273.

If eligible, each study participant will receive a notification letter and will be asked to schedule a BD-1 Visit at their study site. Principal investigators should consider current local public health guidance for administration of COVID-19 vaccines under EUA and marketing authorization (if any) when determining the scheduling priority of participants.

Figure 4: Study Schema (Part 1C-1, Open-label Homologous Booster Dose Observational Phase)

Abbreviations: BD = booster dose; D = day; SoA = Schedule of Assessments

At the BD-1 Visit, each participant will:

- Be encouraged to remain in the ongoing study,
- Sign a revised ICF that includes both updated safety information relevant to the ongoing study and a BD, and the option to receive a BD,
- Be given the option to receive a BD consisting of a 50 µg dose of mRNA-1273,
- Be counseled about the importance of continuing other public health measures to limit the spread of disease including social distancing, wearing a mask, and hand-washing.

At the BD-1 Visit, participants who request a BD and are eligible will have the following study site visits and complete scheduled activities (subject to investigational vaccine availability) according to the Part 1C-1 Supplemental SoA:

- BD-1 Visit: Participants will receive a single 50 µg dose of mRNA-1273,
- BD-1a Visit: All participants who chose to receive BD, Day 4, 3 days after BD on Day 1,
- BD-2 Visit: Day 29, 28 days after the BD on Day 1,

- BD-3 Visit: Day 181, 180 days after the BD on Day 1,
- BD-4 Visit: Day 361, 360 days after the BD on Day 1.

Participants that crossed over from placebo to mRNA-1273 and decline BD will continue with Part 1B SoA ([Table 12](#)).

Participants that received mRNA-1273 in Part 1A and decline BD will continue with in Part 1A SoA ([Table 10](#)).

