8.5.6.2. Part 1C-2 – Heterologous Booster Phase Analysis

Heterologous Booster Phase analysis will be performed in participants who receive mRNA-1273 50 µg in Part 1C-2. Safety, immunogenicity endpoints, and incidence of COVID-19 and SARS-CoV-2 infection will be summarized descriptively, and by prebooster SARS-CoV-2 status if applicable.

In the Heterologous Booster Phase safety analysis, the number and percentage of participants with unsolicited AEs, severe AEs, treatment-related AEs, SAEs, MAAEs, AESIs, and AEs leading to discontinuation from the study participation in Part 1C-2 will be summarized.

The number and percentage of participants with any solicited local AR, with any solicited systemic AR, and with any solicited AR during the 7-day follow-up period after the BD will be provided.

In the Heterologous Booster Phase immunogenicity analyses, the GM titers or levels for specific nAb and bAb (against the ancestral strain or against specific circulating variants of concern), with corresponding 95% CI will be provided at BD-Day 1, BD-Day 29, BD-Day 181, and BD-Day 361. Geometric mean fold rise relative to BD-Day 1 will be summarized with 95% CIs at BD-Day 29, BD-Day 181, and BD-Day 361. The 95% CIs will be calculated based on the t-distribution of the log transformed values then back transformed to the original scale.

Descriptive summary statistics including median, minimum, and maximum will also be provided for GM value and GMFR. The SRR and category of at least 2-fold rise relative to BD-Day 1 will be summarized with numbers and percentages of participants. The immunogenicity descriptive summaries will be provided in the PP Immunogenicity Subset who have available nAb and bAb assay results for the specified timepoints.

In the Heterologous Booster Phase, the incidence rate of the first occurrence of symptomatic COVID-19 starting 14 days after the BD will be summarized by prebooster SARS-CoV-2 status. The incidence rate of SARS-CoV-2 infection (symptomatic or asymptomatic infection) starting 14 days after the BD, and the incidence rate of asymptomatic SARS-CoV-2 infection starting 14 days after the BD will be summarized. The incidence rates with 95% CI will be computed adjusting for person-years starting from BD-Day 1 in Part 1C-2.

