8.7. Study Analyses

8.7.1. Interim Analyses

More than one IA may be performed.

- The IA of immunogenicity, safety, and efficacy will be performed after Day 57 immunogenicity data are available for the Immunogenicity Subset and at least 1500 participants (1,000 participants receiving mRNA-1273) have completed Day 57 (1 month after Dose 2, Part 1A). This IA will be considered the primary analysis of immunogenicity for Part 1A.
- An IA of immunogenicity and safety may be performed after all or subset of participants who receive BD have completed BD-Day 29 after the BD in Part 1C-1.
- An IA of immunogenicity and safety may be performed after all or subset of participants who receive heterologous BD have completed BD-Day 29 after the BD in Part 1C-2.
- An IA of immunogenicity and safety may be performed after Day 57 immunogenicity data are available after all or a subset of participants in Part 2 have completed Day 57 (1 month after Dose 2, Part 2).
- An IA of immunogenicity and safety may be performed after all or a subset of participants who receive 50 μ g mRNA-1273.222 dose have completed Day 29 (1 month after Dose 1).
- At the Sponsor's discretion, a CSR may be developed for an IA.

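### Booster-phase symptomatic COVID-19 and RT-PCR-dated infections are counted from 14 days after the booster but person-years from BD-Day 1, so these rates are understated, by about 4–6% at full follow-up

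*Protocol*

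**What the plan says.** Protocol Section 8.5.6.1 (Part 1C-1) defines the numerators first. For symptomatic disease, "the incidence rate of the first occurrence of symptomatic COVID-19 starting 14 days after the BD will be summarized by prebooster SARS-CoV-2 status". The following sentence sets the same 14-day start for any SARS-CoV-2 infection and for asymptomatic infection: "the incidence rate of asymptomatic SARS-CoV-2 infection starting 14 days after the BD will be summarized". The denominator comes next: "The incidence rates with 95% CI will be computed adjusting for person-years starting from BD-Day 1 in Part 1C-1".

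Section 8.5.6.2 has the same structure for the heterologous booster: "The incidence rates with 95% CI will be computed adjusting for person-years starting from BD-Day 1 in Part 1C-2". The synopsis repeats both rules under its Part 1C-1 and Part 1C-2 booster-phase analysis headings. The case start agrees with the exploratory endpoints in Section 2, Table 1: "The incidence of the first occurrence of symptomatic COVID-19 starting 14 days after BD of mRNA-1273". Nothing elsewhere in the protocol takes the first 14 days out of the person-time.

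**The concern.** A person-time rate needs a numerator and a denominator that cover the same period at risk. Here the denominator opens on the day of the booster and the numerator opens 14 days later. For an event with a known date, such as symptomatic COVID-19 or a positive RT-PCR, the first 14 days add exposure but cannot add a case. A participant who leaves before day 14 adds only exposure.

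The error always runs towards a lower rate after the booster. The rates are reported as absolute single-arm figures with confidence intervals, so no concurrent control arm offsets it. Its relative size also depends on length of follow-up, so rates from different data cuts, or from cohorts followed for different times, would carry different amounts of it.

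This is not a detail left open for the statistical analysis plan, because the protocol itself fixes the start of person-time for the booster phase.

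**Working it through.** The protocol gives no booster-phase incidence figure to reproduce, so the check is of the rule itself.

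**Inputs**
- Start of case counting: 14 days after the booster (Sections 2, 8.5.6.1 and 8.5.6.2).
- Start of person-time: BD-Day 1 (Sections 8.5.6.1 and 8.5.6.2).
- Planned follow-up: "BD-4 Visit: Day 361, 360 days after the BD on Day 1" (Section 3.1.1.3), so F = 360 days.
- Assumed for illustration: other values of F, hazards of 0.05 to 1.0 per person-year, 1,000 boosted participants, and the case counts. Section 8.3.1.2.1 expects more than 1,000 boosted in Part 1C-1.

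**Step 1: fixed follow-up, no censoring**

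With c cases among N participants, the rate as written is c / (N × F) and the aligned rate is c / (N × (F − 14)). Their ratio is (F − 14) / F, so the shortfall is 14 / F.

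| F (days) | Shortfall 14/F | Aligned ÷ as written |
|---|---|---|
| 360 | 3.9% | 1.040 |
| 180 | 7.8% | 1.084 |
| 90 | 15.6% | 1.184 |

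**Step 2: constant hazard λ, time stopped at first event**

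- Expected cases per participant from day 14: exp(−14λ) − exp(−Fλ).
- Person-time from day 0: (1 − exp(−Fλ)) / λ.
- Person-time from day 14, among those still event-free: (exp(−14λ) − exp(−Fλ)) / λ.
- Shortfall: (1 − exp(−14λ)) / (1 − exp(−Fλ)).

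| Hazard per person-year | F = 360 | F = 180 |
|---|---|---|
| 0.05 | 4.0% | 7.9% |
| 0.2 | 4.3% | 8.1% |
| 0.5 | 4.9% | 8.7% |
| 1.0 | 6.0% | 9.7% |

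**Step 3: size beside sampling error**

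For 1,000 participants and 360 days, person-time is 1,000 × 360 / 365.25 = 985.6 years as written and 1,000 × 346 / 365.25 = 947.3 years aligned. With 50 assumed cases and exact Poisson limits, the rate per 1,000 person-years is 50.7 (37.7 to 66.9) as written and 52.8 (39.2 to 69.6) aligned. With no cases the estimate stays at zero, but the upper limit is 3.7 instead of 3.9.

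**Step 4: does the reasoning cover all three outcomes?**

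Table 1 lets asymptomatic infection be identified by RT-PCR, by nucleocapsid antibody, or by both. Tables 13 and 14 schedule blood at BD-Day 1, 29, 181 and 361 and a routine swab only at BD-Day 1. A conversion first seen at BD-Day 29 places the infection somewhere between BD-Day 1 and BD-Day 29, possibly before day 14. If such conversions count, early exposure does generate cases, and Steps 1 and 2 do not apply to them. For Part 1A, Table 1 names Day 57 as the first visit at which conversion counts; the booster endpoints name no such visit.

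**The case against.** The best reply is that little depends on these rates. They are exploratory, summarized descriptively and untested; effectiveness is inferred from antibody geometric means and seroresponse. At planned follow-up the shift is small beside the confidence interval. The only planned split is by prebooster SARS-CoV-2 status, where both strata have the same schedule and nearly the same offset. All of this stands. It limits the consequence but does not make the mismatch correct.

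The serology objection also stands. It is tempting to say that every booster-phase infection rate is biased low and that one new start date cures all of them. The documents do not support that, because a BD-Day 29 conversion can arise from the first 14 days. Deleting those days for such cases could push the rate too high.

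A reader might also infer a 50% understatement at the first booster interim analysis, since 14 / 28 = 0.5. Section 8.7.1 does not support this as a predicted result: "An IA of immunogenicity and safety may be performed after all or subset of participants who receive BD have completed BD-Day 29". That interim analysis covers immunogenicity and safety, whereas the Part 1A interim analysis in the same section adds efficacy. BD-Day 29 is also the minimum follow-up for those included, not everyone's follow-up at the cut.

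Nor does the point extend to Part 3. Section 8.5.8 mentions adjustment for person-years without fixing a start, so it states nothing wrong.

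**Conclusion.** The point holds for symptomatic COVID-19 and for infections dated by RT-PCR in Parts 1C-1 and 1C-2. As written, these rates and their confidence limits are understated by about 14 / F: about 4–6% at 360 days, about 8–10% at 180 days, and more at earlier cuts if incidence is reported there. The ranges assume constant hazards of 0.05 to 1.0 per person-year and no dropout before F. The direction is certain for any non-zero count; with no cases only the upper limit moves.

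For infections known only from seroconversion, neither the direction nor the size can be stated until the protocol says whether a BD-Day 29 conversion counts. No hypothesis test, alpha allocation or coprimary conclusion is affected. This is a definite error of modest size in exploratory rates.

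**What to change.** Change the person-time sentence in four places: Section 8.5.6.1, Section 8.5.6.2, and the two corresponding booster-phase paragraphs of the synopsis. Suggested text: for symptomatic COVID-19 and RT-PCR-dated infection, person-years start 14 days after the booster and include only participants still in follow-up at that time without an earlier qualifying event.

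Add one sentence for infections identified only by nucleocapsid seroconversion, matching the risk period to the detection interval. It should state whether a conversion first seen at BD-Day 29 counts as a case and start the person-time for that outcome accordingly.

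No change to Part 3 is needed on this ground. The cost is one replaced sentence in each of the four places, the serology sentence, and a small programming change; no new data are required. Section 8 already allows changes to exploratory analyses to be listed and explained in the statistical analysis plan or the study report, so the correction can be documented there.

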8.5.6.2. Part 1C-2 – Heterologous Booster Phase Analysis

Heterologous Booster Phase analysis will be performed in participants who receive mRNA-1273 50 µg in Part 1C-2. Safety, immunogenicity endpoints, and incidence of COVID-19 and SARS-CoV-2 infection will be summarized descriptively, and by prebooster SARS-CoV-2 status if applicable.

In the Heterologous Booster Phase safety analysis, the number and percentage of participants with unsolicited AEs, severe AEs, treatment-related AEs, SAEs, MAAEs, AESIs, and AEs leading to discontinuation from the study participation in Part 1C-2 will be summarized.

The number and percentage of participants with any solicited local AR, with any solicited systemic AR, and with any solicited AR during the 7-day follow-up period after the BD will be provided.

In the Heterologous Booster Phase immunogenicity analyses, the GM titers or levels for specific nAb and bAb (against the ancestral strain or against specific circulating variants of concern), with corresponding 95% CI will be provided at BD-Day 1, BD-Day 29, BD-Day 181, and BD-Day 361. Geometric mean fold rise relative to BD-Day 1 will be summarized with 95% CIs at BD-Day 29, BD-Day 181, and BD-Day 361. The 95% CIs will be calculated based on the t-distribution of the log transformed values then back transformed to the original scale.

Descriptive summary statistics including median, minimum, and maximum will also be provided for GM value and GMFR. The SRR and category of at least 2-fold rise relative to BD-Day 1 will be summarized with numbers and percentages of participants. The immunogenicity descriptive summaries will be provided in the PP Immunogenicity Subset who have available nAb and bAb assay results for the specified timepoints.

In the Heterologous Booster Phase, the incidence rate of the first occurrence of symptomatic COVID-19 starting 14 days after the BD will be summarized by prebooster SARS-CoV-2 status. The incidence rate of SARS-CoV-2 infection (symptomatic or asymptomatic infection) starting 14 days after the BD, and the incidence rate of asymptomatic SARS-CoV-2 infection starting 14 days after the BD will be summarized. The incidence rates with 95% CI will be computed adjusting for person-years starting from BD-Day 1 in Part 1C-2.

8.5.7. Part 2 Analysis

Part 2 safety and immunogenicity endpoints will be summarized descriptively.

In the safety analysis, the number and percentage of participants with unsolicited AEs, severe AEs, treatment-related AEs, SAEs, MAAEs, AESIs, and AEs leading to discontinuation from the study participation in Part 2 will be summarized.

The number and percentage of participants with any solicited local AR, with any solicited systemic AR, and with any solicited AR during the 7-day follow-up period after each injection will be provided.

In the immunogenicity descriptive analyses, the GM value for specific Ab (against the ancestral strain or against specific circulating variants of concern) with corresponding 95% CI, and GMFR from baseline with 95% CI will be provided by timepoint. GM and GMFR 95% CIs will be calculated based on the t-distribution of the log transformed values then back transformed to the original scale. Descriptive summary statistics including median, minimum, and maximum will also be provided for GM and GMFR. The SRR and category of at least 2-fold rise from baseline by timepoint will be summarized with numbers and percentages of participants. The immunogenicity descriptive summaries will be provided in the PP Immunogenicity Subset who have available nAb and bAb assay results for the specified timepoints.

8.5.8. Part 3 Analysis

In the safety analysis, the number and percentage of participants with unsolicited AEs, severe AEs, treatment-related AEs, SAEs, MAAEs, AESIs, and AEs leading to discontinuation from the study participation in Part 3 will be summarized.

The number and percentage of participants with any solicited local AR, with any solicited systemic AR, and with any solicited AR during the 7-day follow-up period after each injection will be provided.

In the Part 3 immunogenicity analysis, for the coprimary endpoints (Ab GM value against Omicron BA.4/BA.5 and the ancestral strain at Day 29 after Dose 1 of 50 µg mRNA-1273.222 in baseline SARS-CoV-2 positive adolescents in Study P203 compared with those at Day 57 after Dose 2 of 100 µg mRNA-1273 in baseline SARS-CoV-2 negative adults 18 to 25 years of age in Study P301), the following analyses will be performed for the respective hypothesis testing:

An ANCOVA model will be carried out with Ab value at Day 29 in P203 and Ab value at Day 57 in P301 as a dependent variable and a group variable (baseline SARS-CoV-2 positive adolescents in Study P203 and baseline negative SARS-CoV-2 young adults in Study P301) as the fixed variable, where a covariate may be included in the model (to be specified in the SAP). The GM value at Day 29 in P203 and the GM value at Day 57 in P301, and respective GMR for P203 compared to P301 will be estimated from the model. A corresponding 2-sided 95% CI of GMR estimated from the ANCOVA model will be provided to assess the difference in immune response after Dose 1 (Day 29) for the adolescents in Study P203 compared to that after Dose 2 (Day 57) in the young adults (18 to 25 years of age) in Study P301.

The first coprimary endpoint, superiority of immune response to mRNA-1273.222 against Omicron BA.4/BA.5 after Dose 1 compared to mRNA-1273 against Omicron BA.4/BA.5 after Dose 2 as measured by GM value will be considered demonstrated if the respective GMR 95% CI lower bound is >1 based on a superiority margin of 1.

The second coprimary endpoint, noninferiority of immune response to mRNA-1273.222 against ancestral strain after Dose 1 compared to mRNA-1273 against the ancestral strain after Dose 2 as

measured by GM value will be considered demonstrated if the respective GMR 95% CI lower bound is >0.667 based on the noninferiority margin of 1.5. The GM value and GMR with specified CIs will also be summarized using t-distribution of the log transferred values and then back transformed to the original scale, and by baseline SARS-CoV-2 status.

Secondary endpoints evaluating SRR with 95% CIs (using Clopper-Pearson method) will be summarized by baseline SARS-CoV-2 status at Day 29 in adolescents in Study P203, and at Day 57 in adults in Study P301. Seroresponse at subject level is defined as Ab value change from baseline (preDose 1) below the LLOQ to $\geq 4 \times$ LLOQ, or at least a 4-fold rise if baseline is \geq LLOQ. The SRR and category of at least 2-fold rise from baseline by timepoint will be summarized with numbers and percentages of participants.

The GM values for specific nAb and bAb, with corresponding 95% CIs, and GMFR from baseline with 95% CIs will be summarized by timepoint. The 95% CIs will be calculated based on the t-distribution of the log transformed values then back transformed to the original scale. Descriptive summary statistics including median, minimum, and maximum will also be provided.

The incidence rate of the first occurrence of symptomatic COVID-19 14 days after Dose 1 will be summarized. The incidence rates with 95% CIs will be computed adjusting for person-years.

